It is standard of care for infants discharged from the JHACH NICU to see their primary care provider (PCP) within a day or two of discharge. Follow-up will be provided by an IRB approved study team JHACH Pediatrician, and will take place within one or two days after discharge then weekly for 4 weeks after discontinuation of methadone treatment.

G. Off-treatment Criteria:

Principal Investigator: [name], MPH

Application Number: IRB00107690

Off-treatment is defined as an infant who no longer qualifies for discharge home on methadone – i.e. requiring adjuvant pharmacological therapy or re-admission to the hospital while still on methadone

1. Addition of adjuvant therapy:

It is common for infants suffering from NAS to require the addition of an adjunct therapeutic agent for control of symptoms. This second-line agent varies among institutions but consists often of phenobarbital.

If demonstration project participants have uncontrolled NAS symptoms (defined as a 24-hour Finnegan score average ≥ 11 despite comfort measures and maximal methadone dosing – i.e. 0.1 mg/kg given every 4 hours), the infant will be placed on phenobarbital, the standard of care at JHACH NICU. Such infant will be off-treatment from the study i.e. will not qualify for subsequent discharge home prior to discontinuation of methadone. Maternal assessments of bonding and depression will remain ongoing. There will be no home nursing visits.

2. Re-admission to the JHACH NICU:

It is common for infants suffering from NAS not to tolerate weaning off medication. Re-escalation during that phase is common. If during the weaning phase, infant's Finnegan scores are > 8 on 2 consecutive scores despite comfort measures, the dose of methadone will be increased to the previous dose at which the patient's symptoms were well controlled.

If an infant requires consecutive re-escalation of medication with no control of symptoms (i.e. 24 hour Finnegan scores > 6), such infant will be re-admitted to the hospital.

- for infants who were discharged home on a dose of methadone that is < 0.04 mg/kg, such infant will be re-admitted to the hospital if consecutive re-escalation of methadone are required and infant reaches a dose of 0.05 mg/kg.

- for infants discharged home at a dose of 0.04 mg/kg, who do not tolerate weaning at home and who require dose escalation, the dose will be increased in 2 increments per protocol to a value of 0.07 mg/kg before re-admission to the hospital.

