Upon re-admission to the JHACH NICU, such infant will no longer qualify for discharge home while on methadone medication and will be considered off-treatment. There will be no further home nursing visits. Analysis of maternal assessments of bonding and depression will remain ongoing.

Study related questionnaires to assess bonding and depression:

A. The Postpartum Bonding Questionnaire (PBQ) and the Edinburgh Postnatal Depression Scale (EPDS) will be given to mothers of methadone-treated and non-treated infants at 2 different time points:

Principal Investigator: [name], MPH

Application Number: IRB00107690

- i. After initiation of methadone and prior to discharge during the weaning phase of narcotic treatment and
- ii. At 6 to 8 weeks. The 6 to 8 weeks questionnaires will be administered either through a home visit by Kids Home Care or via a phone interview conducted by a study member

B. Safety plan for handling survey responses related to the Postpartum Bonding Questionnaire:

[name], a licensed psychologist and Co-Investigator on this study, will oversee the interpretation of the questionnaire as this is her area of expertise. If [name] is not available, [name] (licensed psychologist) will oversee the interpretation of the questionnaire. For the PBQ, scores are summated for each factor, with a high score indicating concern for bonding. Any woman who reports a high score on any of the factors (greater than 11 for factor 1, greater than 16 for factor 2, greater than 9 for factor 3, or greater than 2 for factor 4) will be counselled about the results by a clinical social worker, part of the study team. The counselling will happen no later than 24 hours after the mother is identified. The study member will contact the woman, will suggest that she seeks further care, and will provide her with the name and telephone number of resources in the community to seek further follow-up. In addition, the social worker will ask the woman whether she may share this information with her obstetrician to help her better manage her obstetrical care. (All women have signed a HIPAA authorization upon enrollment). If she agrees, the treating obstetrician will be notified. A social worker pre-identified by operation PAR will be notified as well within 24 hours of identifying bonding-related concerns.

C. Safety plan for handling survey responses related to the Edinburgh Postnatal Depression Scale:

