JHACH admitted and average of 131 NAS infants in recent years who required pharmacological treatment for NAS. Approximately 30% of those mother/infant dyads were residents of PAR. We anticipate to enroll 25 mother/baby dyads into the methadone treatment group and 25 mother/baby dyads into the control group for a total of 100 participants. Both the mother and infant are research participants. Those infant participants are defined as 1) needing methadone or other opiate treatment, 2) transitioning to home care, and 3) successfully weaning off medication.

This number has been extrapolated taken into account the following projections/assumptions: 1) not all mothers staying at PAR will meet criteria for participation, and 2) polydrug use may be discovered at the time of delivery thus excluding from participation, and 3) 20-40% of infants enrolled may need adjunct second line therapy.

b. Blinding, including justification for blinding or not blinding the trial, if applicable.

This is a demonstration study with no blinding of subjects involved.

c. Justification of why participants will not receive routine care or will have current therapy stopped.

All infants will continue to receive routine hospital care. Methadone treatment is approved by the FDA, and endorsed by the AAP for inpatient and outpatient treatment of infants with NAS. While methadone is not used as the standard of care at JHACH NICU for infants with NAS at birth, it is still used for later iatrogenic withdrawal in the NICU and other intensive care units in the hospital.

d. Justification for inclusion of a placebo or non-treatment group. N/A Will need to justify this as a comparison groups has been included

e. Definition of treatment failure or participant removal criteria.

As delineated above, infants will be off-treatment from the demonstration project if 1) they require the addition of a second-line of pharmacological treatment or 2) they require re-admission to the

Principal Investigator: [name], MPH

Application Number: IRB00107690

hospital. Data will still be collected until final hospital discharge for these infants and the maternal assessments of bonding and depression will remain ongoing. .

Other Indications for participant off-study:

- a. Parent withdraws informed consent at any time
 - b. Infant transfers to another hospital.
 - c. Infant experiences an unexpected adverse event deemed related to study intervention

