- a. **Primary outcome variable:** Length of Stay (LOS)

- b. **Additional outcomes of interest to be examined:**

- 1) Maternal bonding measured by the Postpartum Bonding Questionnaire (PBQ);
- 2) Depressive symptomatology measured by Edinburgh Postnatal Depression Scale (EPDS);
- 3) Hospital readmission within 30 days;
- 4) Weight gain of greater than 15% above Birth Weight at 30 days of age;
- 5) Age appropriate development as screened by the Ages and Stages questionnaires.

- c. **Statistical plan including sample size justification and interim data analysis:**

Demographic and clinical characteristics of participants will be summarized using means with standard deviations (SD) or median with interquartile ranges for continuous variables and counts and percentages for categorical variables. The primary outcome, length of stay, will be summarized using mean (SD) or median and interquartile range and will be compared to the comparison group using the t-test or Wilcoxon rank sum test as appropriate. For the secondary outcomes, the scores on the postpartum bonding questionnaire or the Edinburgh Postnatal Depression Scale will be summarized using means (SD) and compared to other patients in the comparison group using independent two-sample t-test. The proportion of participants that are readmitted within 30 days or with a weight gain of greater than 15% above birth weight will be compared to the comparison group using a Chi-squared or Fishers exact test as appropriate. Among the methadone cohort, we will calculate percentage of infants with age appropriate development at 4, 8 and 12 months. We anticipate that 25 mother-child dyads in each group will be available for the study. We expect that the mean LOS in the comparison group will be around 25 days (based on historical data). This sample size will allow us to estimate differences in LOS of >4 days with sufficient power (80%) at an alpha of 0.05, assuming a standard deviation of 5 days for both groups.

Early stopping rules:

Infant: requiring therapy with a second drug

Parents: desire to remove the infant from the study at any time or when infant is transferred to another hospital.

7. Risks

- a. **Medical risks, listing all procedures, their major and minor risks and expected frequency:**

Principal Investigator: [name], MPH

Application Number: IRB00107690

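### Length of stay has no rule for a second admission, so NAS re-admission days appear to enter no duration analysis, and the omission falls mainly on the methadone group

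*Combined protocol and SAP*

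**What the plan says.** Section 6, items a to c, names LOS as the primary outcome: "The primary outcome, length of stay, will be summarized using mean (SD) or median and interquartile range", compared between groups by t-test or rank sum test. No start, end or second-stay rule is given. Re-admission within 30 days is a separate outcome, analysed as a proportion. LOS is the only duration outcome in the section.

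Elsewhere LOS is used as time to discharge home. The Background projects at most 14 NICU days followed by 10 days of home care. The rationale for amending the Table 1 regimen says that sending infants home on medication minimises LOS.

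The two groups leave hospital at different points. The Abstract says NAS infants have historically stayed until all narcotics are weaned. Methadone infants may go home at 0.04 mg/kg or below (C. Discharge home). Under G. Off-treatment Criteria, item 2, those who fail at home through repeated re-escalation are re-admitted, and then "such infant will no longer qualify for discharge home while on methadone medication and will be considered off-treatment". The same item says: "It is common for infants suffering from NAS not to tolerate weaning off medication. Re-escalation during that phase is common".

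The item on treatment failure and participant removal adds, for infants who go off treatment: "Data will still be collected until final hospital discharge for these infants". Section 6 assigns those data to no outcome.

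**The concern.** One clinical event, failure to wean, is counted differently in the two groups. Under usual care it happens before discharge and adds days to LOS. In the methadone group it can happen after discharge, and the hospital days it causes then fall in a second stay that LOS, on its ordinary reading, does not count. An infant sent home at day 14 and re-admitted for a further 7 days would be recorded as a 14-day stay. The error runs in one direction, toward methadone, and sits in the primary comparison of an unblinded, non-randomised study, where the counting rule needs to be fixed before the data are seen.

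**Working it through.** **Inputs.** From Section 6: 25 infants per group ("We anticipate that 25 mother-child dyads in each group will be available for the study"), SD 5 days ("assuming a standard deviation of 5 days for both groups"), a target to "estimate differences in LOS of >4 days", and comparison mean LOS of about 25 days. From the Abstract: a hypothesised methadone LOS below 15 days. From Table 2: Steps 2 to 7 need at least two doses 12 hours apart (1 day each), and Step 8 one dose at a 24-hour interval (1 day). From G, item 2: re-admission is tied to reaching 0.05 mg/kg (Step 3) or 0.07 mg/kg (Step 2), depending on the discharge dose. The re-admission rate is not given.

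**The plan's own figure.** The standard error of the difference is 5 × √(2/25) = 1.414. Normal approximation: 4/1.414 − 1.960 = 0.868, giving power 80.7%. The noncentral t with 48 df gives 79.1%. The stated power ("with sufficient power (80%) at an alpha of 0.05") reproduces as a two-sided calculation, so the sample-size arithmetic is not at fault.

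**Days omitted per re-admission (D).** Steps 2 to 8 take 7 days and Steps 3 to 8 take 6, if the minimum doses of the re-admission step are given in hospital. Adding 72 hours of in-hospital observation gives 10 and 9; that addition is an assumption. With a 14-day index stay, total hospital time is 20-21 days (23-24 with observation), against about 25 in the comparison group.

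**Effect on the group mean.** With k re-admissions among 25, the hidden mean is k × D/25. For k = 1 this is 0.24-0.28 day at D = 6-7 and 0.36-0.40 at D = 9-10.

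**False benefit if total hospital days were truly equal.** The index-LOS contrast then has noncentrality (hidden mean)/1.414. Two-sided t-test, SD 5:

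| k of 25 (assumed) | Hidden days, D = 6-7 | Significant | Hidden days, D = 9-10 | Significant |
|---|---|---|---|---|
| 3 | 0.72-0.84 | 8-9% | 1.08-1.20 | 12-13% |
| 5 | 1.2-1.4 | 13-16% | 1.8-2.0 | 24-28% |
| 10 (upper scenario) | 2.4-2.8 | 38-49% | 3.6-4.0 | 70-79% |

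With nothing hidden, the rate is 5%. The table counts rejections in either direction; at most 0.7 percentage point favours the comparison group.

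**If methadone does shorten the index stay.** For re-admission probability r, the true difference in total days is the index difference minus r × D, and the methadone SD becomes √(25 + r(1−r)D²). At D = 9:

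| r (assumed) | 4-day index difference becomes | Power | 10-day index difference becomes | Power |
|---|---|---|---|---|
| 4% | 3.64 | 69% | 9.64 | >99% |
| 10% | 3.1 | 52% | 9.1 | >99% |
| 20% | 2.2 | 27% | 8.2 | >99% |
| 30% | 1.3 | 12% | 7.3 | 99% |

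In the upper scenario (r = 40%, D = 10), the 10-day difference becomes 6.0 with SD √(25 + 0.24 × 100) = 7.0 and power of about 93%.

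**The case against.** No sentence excludes re-admission days. LOS is simply undefined, and the instruction to collect data to final discharge is compatible with counting the whole stay. This stands as far as it goes: exclusion is an inference from how the protocol uses the term and from re-admission being a separate yes/no outcome. A reader might infer that the plan rules these days out; it does not. The repair is the same either way, because an undefined primary outcome leaves the choice open until after the data are seen.

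Failures are also not invisible. Thirty-day re-admission is tested, and hospitalisation of a methadone infant meets the serious adverse event definition, with start and stop dates recorded. True, but a proportion reported beside LOS does not correct the LOS contrast.

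A reader might take the protocol to say that re-admission is common. It says so only of intolerance to weaning and of re-escalation. Re-escalation is first handled at home, and discharge requires 72 hours without one. The re-admission rate is therefore unknown.

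The 72-hour observation is written for the home, and a re-admitted infant is barred from discharge only while on methadone. In-hospital observation is plausible, since home nursing visits end at re-admission and the protocol describes the observation as in accordance with the hospital's standard of care, but it is not stated. The documented floor is 6-7 days.

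Finally, Accrual describes the enrolled infants as successfully weaning off medication, so it is unclear whether re-admitted infants are analysed at all. The k/25 figures assume that they are.

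**Conclusion.** The point holds and should be addressed. On its ordinary reading, index LOS understates hospital time for re-admitted infants by at least 6-7 days each, mainly in the methadone group, and no planned duration analysis recovers those days. Infants who are not re-admitted are unaffected, as are those who need phenobarbital before discharge, since they stay in hospital until off methadone.

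The group-level size depends on an unstated re-admission rate: 0.7-1.2 days for three re-admissions, 1.2-2.0 for five, and 2.4-4.0 for ten. That is material beside the 4-day difference used for power.

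Two stronger conclusions are not supported. The first is that a false positive is likely: the 79% figure needs ten of 25 infants re-admitted for 10 days each and no true difference in total days. The second is that the hypothesised benefit would vanish: a 10-day index difference leaves 7.3-9.6 days at re-admission rates of 4-30% and D = 9, with power still about 99% or more. The distortion is to the size of the effect, and it matters most when the true difference is near 4 days.

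**What to change.** In Section 6.a and 6.c, define when LOS starts and ends. Pre-specify total NAS inpatient days, index stay plus NAS re-admissions, over a fixed window (for example to a stated age), counted alike in both concurrent groups. State that off-treatment and re-admitted infants stay in the analysis, and reconcile this with the participant definition under Accrual. Use total days as the primary LOS measure, or at least as a key analysis reported beside index LOS. Keep index LOS for the historical comparison, because the documents give no historical re-admission days.

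The cost is modest. Data to final discharge are already planned for off-treatment infants. For comparison infants, re-admission dates must be abstracted from the record over the same window. The LOS advantage may look smaller. The power statement should say which LOS definition it refers to: its 25-day anchor is historical LOS, and total days will have a larger SD if some infants return. No change to dosing, discharge or re-admission rules is involved.

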Protocol Title: Methadone Demonstration Project

NCT03134703

Protocol v5: 02.02.2018

JHM IRB - eForm A – Protocol

- **Use the section headings to write the JHM IRB eForm A, inserting the appropriate material in each. If a section is not applicable, leave heading in and insert N/A.**
- **When submitting JHM IRB eForm A (new or revised), enter the date submitted to the field at the top of JHM IRB eForm A.**

1. Abstract

- a. Provide no more than a one page research abstract briefly stating the problem, the research hypothesis, and the importance of the research.

The Problem:

Infants who are born to mothers taking or abusing opiates frequently suffer from neonatal abstinence syndrome (NAS) after birth. They often have withdrawal symptoms which can be life-threatening if untreated. The American Academy of Pediatrics (AAP) recommends non-pharmacologic treatment as first-line therapy, followed by opioid replacement for severe cases. The pharmacologic treatment usually takes place within the hospital setting. Such approach often incurs prolonged hospitalization and significant financial burden. It also creates barriers to adequate maternal/infant bonding with potential deleterious consequences for the infant's long term emotional and societal outcomes.

The Research Hypothesis: Among Neonatal Intensive Care Unit (NICU) infants diagnosed with NAS and requiring pharmacological treatment, those who are treated with methadone will have a shorter Length of Stay (LOS) of less than 15 days as compared to the average length LOS of 25 days of NAS infants admitted in recent years at Johns Hopkins All Children's Hospital (JHACH) NICU.

The Importance of the Research:

Infants suffering from NAS are historically cared for in the hospital setting and are not discharged home until all narcotic medications have been weaned off. Such prolonged hospital stay invariably equates to prolonged separation of mother and baby. Consequently, infants suffer from the absence of a care giver who could provide constant comforting techniques which are the mainstay of treatment of infants with NAS. This in turn leads to further prolongation of the hospital stay and impaired mother-infant bonding.

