NAS is manifested by central nervous system irritability (high pitch and inconsolable crying, irritability and sleep disturbances), autonomic nervous system over-reactivity (sweating, yawning, sneezing), gastrointestinal manifestations (poor feeding, emesis and loose stools) and respiratory distress (tachypnea and nasal congestion) (Finnegan 1975; Finnegan, 1976; Kaltenbach, 1986; Desmond 1975). The standard of care is to treat these infants with a slow taper of opioid but to date there is no established gold standard for that taper (Cochrane, 2010). The lack of high-quality research in the treatment of NAS has led to wide variations in medications and protocols (Patrick, 2014; O'Grady, 2009; Sarkar, 2006) and data on changes in the utilization of NICU resources in the treatment of affected infants are lacking (Tolia, 2015).

For the time frame July 1, 2013 through September 30, 2014, 300 infants with NAS have been cared for at the Johns Hopkins All Children's Hospital (JHACH) NICU with an average length of stay of 30 days. The average length of stay has recently decreased to 22-25 days with implementation of strict management guidelines and protocols. Accounting for an average daily cost of \$2062.50, the burden translates into medical costs averaging \$48,468.75 per infant. With the proposed model involving methadone treatment, we anticipate at most 14 days of care in the NICU at a cost of \$28,875.00, followed by 10 days of home care at an anticipated cost of \$190/day for a total cost of \$30,775. This is an anticipated reduction in cost of \$17,693.75 per patient.

The prolonged stay has other social and medical impacts – including limitation in parental interaction and bonding, exposure to nosocomial infections, and taking up valuable resources both in terms of personnel and equipment. Once discharged home, these infants are often exposed to inconsistent caregiving, family instability, out of home placements, chronic stress, abuse, neglect and poverty – all of which affect their health and development, thus incurring even greater societal costs. To date, there are no published data on the in-home pharmacologic treatment of these infants.

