- e) Discharge home when stable on methadone treatment for continued home care. Stability is defined as 1) a maximal dose of methadone of 0.04 mg/kg at the time of discharge (Step 4 of Table 2), and 2) a history of successful weaning of methadone for a least 3 days prior to discharge;
- f) Twice daily nursing visits in the home after discharge from the NICU for Finnegan scoring and administration of methadone along with general nursing assessment until 48 hours after total weaning of medication is achieved;
- g) Provision of an electronic tablet to the mother to facilitate teleconferencing;
- h) Face-to-face teleconferencing between the mother/infant and Kids HomeCare RNs versed in the care of NAS infants. Such virtual assessment will take place every 3-4 hours and will serve to obtain Finnegan scoring and assess infant. It will continue until 48 hours after total weaning of medication is achieved. After discontinuation of medication, Finnegan scores will be assessed when infant is awake and feeding (most of the Finnegan scoring items are obtained by history, assessment of infant's tone and tremors will be performed by the mother and witnessed by the nurses);
- i) Social work home assessment upon discharge to the home. Child Protective Investigator (CPI) clearance of the home prior to discharge;
- j) Follow-up home visit by the Kids Home Care RN 2 to 3 days after medical treatment is complete;
- k) Follow-up with IRB approved study team JHACH Pediatrician, at his/her JHACH outpatient office 2 to 3 days after discharge home then weekly until 4 weeks after discontinuation of medication; If infant remains on medication for longer than a week after the initial pediatrician's visit, additional visits will be scheduled on a weekly basis until discontinuation of medication;
- l) Home visit or phone interview by the Kids Home Care registered nurse at 4 months, 8 months and 12 months to screen development using Ages and Stages-based questionnaires (ASQ) (Squires, 1997).

B. Methadone treatment:

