The rationale for amending that protocol relates to the reported premature initiation of Phenobarbital as adjunct therapy. Most protocols call for the initiation of adjunct therapy when first line medication fails (i.e. reaching maximal doses or requiring multiple re-escalations of dosing). In Table 1 however, phenobarbital initiation happens instead during the weaning process. Accordingly, a rather large number of infants get started and discharged home on phenobarbital (22.6%).

Our goal is to introduce second-line treatment when truly indicated (i.e. when maximal safe therapy fails) and to minimize discharge home on medication, as this approach, while minimizing the LOS, allows for infants to remain on medication for an indeterminate length of time.

Principal Investigator: [name], MPH

Application Number: IRB00107690

Demonstration Study Methadone Protocol

Initiation:

Initiate protocol for infants with 2 consecutive Finnegan scores > 8. Starting dose is 0.1 mg/kg/dose Q 6 hours (Table 2 - Step 1). As per hospital policy, medications may be given +/- 1 hour from scheduled administration time

Weaning:

Table 2. Initiation and weaning of methadone			
Step	Methadone Dose (mg/kg)	Interval	Minimum Number of Doses
Step 1	0.1	Q6 h	8
Step 2	0.07	Q12 h	2
Step 3	0.05	Q12 h	2
Step 4	0.04	Q12 h	2
Step 5	0.03	Q12 h	2
Step 6	0.02	Q12 h	2
Step 7	0.01	Q12 h	2
Step 8	0.01	Q24 h	1

Initial weaning: wean after 48 hours of stable scores (i.e. 2 consecutive 24 hour Finnegan score averages < 8)
Subsequent weaning: Wean to the next step if the 24 hour Finnegan score average is < 8;
If the 24-hour Finnegan score average is 8-10, do not wean;
If the 24-hour Finnegan score average is ≥ 11, follow escalation below.

Table 2 Escalation:

- Escalation will take place by going back one step in the dosing regimen (i.e. go from Step 5 to Step 4, etc.)
- If infant needs escalation from Step 2 to Step 1, one may consider either going back up the one step to Step 1 or giving an additional methadone dose.
- Weaning will resume after 24 hours of stable scores (i.e. a 24 hour average of <8)
- If infant fails Step 1 above, increase interval of dosing to Q 4 hour (Step 1A in table 3 below)

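### The groups leave hospital under different rules and no outcome measures total time on opioid, so a shorter length of stay cannot be credited to methadone itself

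*Combined protocol and SAP*

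**What the plan says.** LOS is the sole primary outcome (section 6.a). Section 6.c says: "The primary outcome, length of stay, will be summarized using mean (SD) or median and interquartile range", with a t-test or Wilcoxon rank sum test against the comparison group. Planned enrolment is "25 mother/baby dyads into the methadone treatment group and 25 mother/baby dyads into the control group". The precision claim is "This sample size will allow us to estimate differences in LOS of >4 days with sufficient power (80%) at an alpha of 0.05". The variability behind that claim is stated in the same section as "assuming a standard deviation of 5 days for both groups".

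The discharge rules differ:

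- **Usual care.** Section 1 (Abstract) says that infants with NAS have historically been cared for in hospital and "are not discharged home until all narcotic medications have been weaned off". The comparison group's own paragraph under Study Procedures says only that it receives standard of care.
- **Methadone group.** Item A.e under Study Procedures lists "Discharge home when stable on methadone treatment for continued home care" as a study service. Part C (Discharge home) allows this from Step 4 of the eight-step taper, and part E places the off-drug observation at home.

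Section 3 (Background) projects at most 14 NICU days, "followed by 10 days of home care at an anticipated cost of" $190 per day. It gives current LOS as 22–25 days.

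The hypothesis in section 1 and the primary objective in section 2 set infants treated with methadone against past infants and infants given a different narcotic. The other outcomes in sections 2 and 6.b are bonding, maternal depression, 30-day readmission, weight gain, breast milk, development, and several participation and compliance measures. None is a duration of opioid treatment.

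**The concern.** One group may leave hospital on drug and the other may not. The gap in hospital days then contains two things: any difference in how long infants need opioid, and the stretch of treatment that one group completes at home. LOS adds these together, and nothing else in the plan separates them.

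The trial could report a clearly shorter stay when infants were on opioid for a shorter, equal or longer time, and readers could not tell which. Because the hypothesis is phrased by drug, the natural headline would credit methadone with something that the discharge rule alone can produce.

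**Working it through.** **1. The plan's power figure.** Inputs from section 6.c: 25 per group, difference 4 days, SD 5, alpha 0.05 (taken as two-sided). The standard error is 5 × √(2/25) = 1.414, so 4 / 1.414 = 2.828. Power = Φ(2.828 − 1.960) = 80.7%, or 79.1% with the noncentral t. The stated 80% reproduces, and the calculation is not in dispute.

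**2. Days of care on the plan's projection.** Inputs from section 3: at most 14 NICU days, 10 home-care days, current LOS 22–25 days. The cost figures imply $48,468.75 / $2,062.50 = 23.5 days. The ceiling on total care is 14 + 10 = 24 days.

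| Current LOS | Fall in LOS (current − 14) | Change in total days of care (24 − current) |
|---|---|---|
| 22 | 8 | +2 |
| 23.5 | 9.5 | +0.5 |
| 25 | 11 | −1 |

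Fourteen is a ceiling, so shorter inpatient stays would bring some real saving. If home care stays at 10 days, the relocated share of the fall is 10 / (current LOS − inpatient days). Against 25 days and a 14-day stay, that is 10/11 = 91%. The share drops to one half only if the inpatient stay falls to 5 days, since 10 / (25 − 5) = 0.5.

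These are days of care, not opioid days. Hospital days include time before treatment starts, and home days run past the last dose.

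**3. The shift built into the taper.** From Table 2, the shortest uninterrupted course is:

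- Step 1: 8 doses × 6 h = 2 days
- Steps 2–7: 6 × (2 doses × 12 h) = 6 days
- Step 8: 1 day
- Total: 9 days

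Step 4 begins after 2 + 1 + 1 = 4 days. Three days of weaning after the first wean is reached at 2 + 3 = day 5. Discharge is therefore first possible at about day 4–5, which leaves 4–5 drug days at home. With the 72-hour observation in part E, 7–8 days move home. With the 48 hours given in item A.f and the schedule footnote, it is 6–7 days; those passages need reconciling. Either figure exceeds the 4-day detectable difference.

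**4. The LOS test when treatment duration is equal.** Assumptions: the same true treatment duration in both groups, normal, SD 5, 25 per group. The first column is exact noncentral-t power. The 20% and 40% columns come from 20,000 simulated trials in which that share of methadone infants stays in hospital throughout. That range is the adjunct-therapy share given under Accrual; infants who need adjunct therapy cannot go home on methadone (part G).

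| Days moved home | None kept in | 20% kept in | 40% kept in |
|---|---|---|---|
| 4 | 79% | 59% | 36% |
| 7 | 99.8% | 95% | 75% |
| 10 | >99.9% | 99.7% | 92% |

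With none kept in, an assumed SD of 8 gives 86% (7 days) and 99% (10 days); an SD of 10 gives 68% and 93%. In the same simulations a test on total duration rejected in about 5% of trials, as it should.

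**5. What a duration comparison could show.** If the SD of total duration were also 5 (an assumption), power would be about 6% for a 0.5-day difference, 11% for 1 day and 28% for 2 days. The 95% confidence interval would be about ± 2.011 × 1.414 = ± 2.8 days. The added outcome is therefore for estimation; a significance test on it would say little.

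**The case against.** The strongest reply is that moving care home is the declared intervention. Section 1 names discharge on treatment as an aim, section 3 costs the home days openly, and section 8 lists shorter hospitalization, bonding, fewer nosocomial infections and cost as the benefits. Hospital days speak directly to these. The plan does not claim faster recovery, and it describes itself as a non-randomized feasibility study. All of this stands, and LOS can stay primary. It does not answer the missing duration measure or the drug-versus-drug wording.

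Three stronger readings are tempting, and the documents do not support them.

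- A reader might infer that the whole expected reduction is relocation. The 14 days are a ceiling, and the figures come from a cost projection in days of care, so the documents do not establish that.
- A reader might infer that the plan condemns its own approach where, in part B (Methadone treatment), it faults an approach that "allows for infants to remain on medication for an indeterminate length of time". That remark concerns infants discharged on phenobarbital under the source protocol. Here home methadone is nurse-given, with a stepwise wean, a stopping criterion and re-admission criteria.
- A reader might infer that the discharge rule fixes the LOS result. It does not. Infants needing adjunct therapy stay in, the home must be cleared, and the comparison group's discharge rule is inferred from section 1 together with the standard-of-care statement.

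Partial safeguards exist. Readmission within 30 days is compared between groups, and infants taken off treatment are followed to final hospital discharge. Readmission can flag a failed home wean, but it does not measure a slow one.

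**Conclusion.** The point holds as a gap in outcomes and in wording. It does not make LOS invalid as a measure of hospital use. On the plan's figures, most of the expected 8–11 day fall in LOS, and possibly all of it, is a change in place of care, with total days of care changing by about +2 to −1.

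This rests on the section 3 projection, on 10 home-care days, and on comparison infants staying until weaned. The simulation adds equal true durations and an SD of 5. Under those assumptions a positive LOS test is likely with no difference in treatment time: 75% to 99.8% for a 7-day shift, depending on how many methadone infants remain in hospital. A positive LOS result would support a conclusion about the programme. It would not support one about methadone versus another narcotic.

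**What to change.** In sections 6.b and 6.c, add two secondary outcomes for both groups:

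1. Days from first to last opioid dose, inpatient plus home, counting any restart.
2. Total hospital days, re-admissions included, over the same fixed window from birth in both groups, for example to an age covered by the 6–8 week contact. A window of 30 days after first discharge would not serve: on the plan's figures it would close near day 14 + 30 = 44 in one group and 25 + 30 = 55 in the other.

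Report each as a between-group difference with a 95% confidence interval, and state in advance that a non-significant difference will not be read as equivalence. Word the LOS conclusion, and align sections 1 and 2 with it, as the effect of the methadone-plus-home-discharge programme.

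The cost is two more analyses, mostly of data already recorded: home doses are nurse-given, and comparison data come from the chart. Re-admissions elsewhere may need one question at the 6–8 week contact. The headline may look less favourable.

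Two limits remain. Days on opioid are not equal exposure across drugs with different half-lives. Nor do these outcomes remove the non-randomized differences between groups, such as selection of compliant Operation PAR mothers and the extra maternal support.
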